5.1 RECRUITMENT AND SCREENING VISITS

CM-allergic children will be recruited through the clinical services at St Mary's Hospital in London (Imperial College Healthcare NHS Trust) and Niño Jesus Hospital in Madrid, two of the largest tertiary services in Europe. We will also recruit through our local paediatric allergy network in North West London. This study requires frequent visits (approximately every 10-14 days) to the Research Unit, so participants should live relatively local to the unit to minimise travel time and impact on other daily activities.

Potential participants and their families will receive the Study Information either in person, by post or via email, following which the participants will be pre-screened by telephone conversation with their parents, to determine likelihood of persistent CM allergy and thus suitability for this study. Suitable participants will then have an appointment made for a screening visit.

The following will take place at the first screening visit:

- Written informed consent and participant assent.
- Clinical history (including dietary history of CM replacement options) and physical examination
- Skin prick test (SPT) to:
 - commercial extracts of whole CM and casein (ALK-Abelló, Hørsholm, Denmark)
 - titrated SPT to fresh cow's milk (sourced from the UK), using the following dilutions (diluted with sterile saline): 1/10, 1/100, 1/1000, 1/10,000, 1/100,000.
 - SPT may also be undertaken to assess sensitisation to other foods not obviously tolerated by the participant, subject to local clinical policy
- For children with asthma, current asthma status will be assessed by the clinician with respect to the ICON consensus,⁹ lung function testing and completion of a validated asthma control test
- For children with eczema, eczema will be assessed using the SCORAD system¹⁰ (which provides an objective measure of eczema severity) as well as the POEM questionnaire, a validated patient-based symptom assessment.
- For female subjects of who have reached menarche and may be susceptible to become pregnant, a urine pregnancy test will be performed.

The screening visit may take place on the same day as the first baseline food challenge, if requested by the family, subject to local availability of staffing and facilities. Participants will also be asked to provide biological samples (blood/saliva/stool sample) at either the screening or one of the DBPCFC visits.

5.2 DOUBLE-BLIND, PLACEBO-CONTROLLED FOOD CHALLENGE TO COW'S MILK

Participants who fulfil eligibility criteria for the study will undergo a baseline double-blind, placebo-controlled food challenge to CM at enrolment, prior to randomisation. The DBPCFC is established as the gold-standard test of diagnosis of food allergy by international consensus.¹¹ The objectives are to:

- i. confirm the diagnosis of IgE-mediated CM allergy
- ii. determine the threshold of clinical reactivity to CM prior to commencing the study protocol

The DBPCFC will be repeated after each intervention phase to assess for any change in threshold.

Each DBPCFC involves 2 half-day visits, within a 28 day period, with a minimum of 72 hours in between DBPCFC visits (7 days if the first challenge results in a reaction). Participants will receive incremental doses of CM protein or placebo 20-30 minutes apart, and monitored for signs/symptoms of allergic reaction. The challenge is halted once pre-determined stopping criteria have been reached. DBPCFC will be performed according to the international PRACTALL consensus for best practice.¹¹

Doses for DBPCFC will be prepared using a CM protein powder (Protifar, Nutricia Ltd, Wiltshire, UK) with equivalent casein: whey ratio to fresh milk) in a liquid matrix flavoured with Nesquik to maintain blinding. All doses used during the food challenge will be double-checked prior to administration. The order of challenge days (active or placebo control) will be randomized by an independent research associate, using a computer-generated randomization list (www.sealedenvelope.com); the randomisation key will be concealed from the study team until both pair of challenges have concluded.

5.2.1 CLINICAL ASSESSMENT AND CHECKS PRIOR TO DBPCFC

All subjects will be assessed prior to DBPCFC to determine suitability for a challenge, as follows:

- No intercurrent illness (viral or otherwise)
- No exacerbation in allergic symptoms (eczema, asthma, food allergy) in the preceding week.
- No short-acting β 2 agonists used in the past 12 hours
- No recent antihistamine exposure (e.g. cetirizine, loratadine) in the past 48 hours (72 hours for fexofenadine, 5 days for long-acting antihistamine (e.g. chlorphenamine, desloratadine).
- No oral steroids have been taken in the past 2 weeks
- Baseline observations (temperature, blood pressure, heart and respiratory rate, oxygen saturations, PEFR) within the normal range.
- Baseline physical examination must not reveal any significant acute findings.

Challenges will occur on a Challenge Unit with staff fully trained in the management of allergic reactions including anaphylaxis. Emergency equipment (including oxygen and suction) and medication will be checked beforehand, as per local protocol and international criteria for performance of DBPCFC.

5.2.2 DBPCFC AT BASELINE AND FOLLOWING PHASE 1

The challenge will consist of up to eight incremental doses of CM/placebo given at 20-30 minute intervals, followed by an observation period of 2 hours, as shown in table 2.

Published data indicates that the eliciting dose in milk-allergic patients may be lower than for other food allergens. As a safety measure, during the baseline DBPCFC, the dosing interval between the first (0.5mg) and second (3mg) doses will be extended to 60 minutes. The additional 30 minutes will allow for the detection of symptoms in the most sensitive participants, thus limiting the chance of further but unnecessary CM doses being given.

¹¹Sampson HA, Gerth van Wijk R, Bindslev-Jensen C, et al. Standardizing double-blind, placebo-controlled oral food challenges: AAAAI-EAACI PRACTALL consensus report. J Allergy Clin Immunol. 2012;130:1260-74.

The time intervals following other doses may be extended up to one hour at the local investigator's discretion, where the participant may be experiencing an evolving reaction (as a safety measure, to limit the dose which might in turn moderate the symptoms experienced at challenge).

For safety reasons, families will be asked to provide their child with a snack to eat one hour after the last dose has been given or the challenge has been stopped due to reaction. Participants will then be observed for a second hour prior to leaving the research unit. This is to avoid the possibility of the participant experiencing further symptoms outside the hospital when eating for the first time after challenge, something which has been noted in previous studies.

Entry and 6 month DBPCFC to Cow's Milk			
Dose	CM protein (mg)	Approximate equivalent volume of fresh CM (ml)	Minimum time interval after dose
1	0.5	0.015	60 mins at baseline DBPCFC, 20-30 mins for 6m DBPCFC
2	3	0.09	20-30 mins
3	10	0.3	20-30 mins
4	30	0.9	20-30 mins
5	100	3	20-30 mins
6	300	9	20-30 mins
7	1000	30	20-30 mins
8	3000	90	2 hours observation
Cumulative dose	4444	~130	
2 hours observation period following last dose to monitor for signs of reaction			

Table 2. Dosing protocol for DBPCFC to CM.

At the second visit of the baseline DBPCFC, the local investigator may elect to give participants who fail to react at either DBPCFC visit a single dose of cow's milk to a cumulative dose of 8 grams (approximately 250ml CM) in an open unblinded manner, 2 hours after the last challenge dose, to confirm tolerance.

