3.1.2. SECONDARY STUDY OUTCOMES

- Proportion of participants experiencing adverse events classified as mild non-transient symptoms or more severe (see table 9) during CM-OIT (phase 2), in those who have received SLIT pretreatment (group S) compared to the equivalent SLIT dose orally during phase 1 (group O).
- Other safety outcomes in the different treatment groups (withdrawals due to intervention, anaphylaxis rate/adrenaline use)
- Efficacy defined at DBPCFC as the proportion of study participants experiencing:
 - i. No symptoms (or only mild transient symptoms as per table 9) to 8 grams CM protein (approx. 250mls fresh milk) ("Complete desensitisation")
 - ii. No symptoms (or only mild transient symptoms as per table 9) to at least 1.4 grams CM protein (approx. 45mls fresh milk) ("Partial desensitisation")
 - iii. At least a 10-fold increase in eliciting dose (defined as the lowest dose which elicits objective symptoms or signs at challenge).

Efficacy at 6 and 12 months will be compared across all treatment groups (including SLIT pretreatment) vs the equivalent dose administered orally without a sublingual phase (to address hypothesis 2).

- Immunological outcomes (titrated skin prick test, serum IgE) at baseline, 6 and 12 months.
- Change in health-related quality of life (HRQL) measures at 6, 12 and 15 months, as assessed by validated questionnaires (FAQLQ, FAIM, EQ-5D, self-efficacy) in study participants and their parents.

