5.3.2.1. INITIAL ESCALATION DAY

Phase 1 will start with an "escalation day" visit in which up to 7 consecutive doses (starting with 0.01 mg of CM protein) will be given, every 30-60 minutes (Table 4) under medical supervision. Doses will be given either by the sublingual or the oral route according to group allocation.

Participant will be assessed prior to dosing to ensure suitability, as described in section 5.2.1. If a given dose triggers symptoms which cause discomfort to the participant (such as sustained oral itch) or deemed to be significant by the research team, no further doses will be administered on the escalation day.

Participants and/or their family will then be instructed to take the last well-tolerated dose on a daily basis at home, for a minimum of 10 days until the next increase is performed.

PHASE 1 UPDOSING PROTOCOL

Steps	CM protein (mg)	Volume of mix (ml)
Step 1	0.01	0.5
Step 2	0.02	0.5
Step 3	0.04	0.5
Step 4	0.08	0.5
Step 5	0.2	0.5
Step 6	0.4	0.5
Step 7	1	0.5
Step 8	2.5	0.5
Step 9	6	0.5
Step 10	15	0.5
Step 11	30	0.5
Step 12	60	0.5

Table 4: Updosing protocol for phase 1 CM immunotherapy pretreatment

Each step will be administered daily at home for a minimum of 10 days. Once the target dose is achieved (step 12), participants will continue this dose on a daily basis for a target of 16 weeks. The duration of Phase 1 will vary from participant to participant, with the aim of achieving Step 12 within 12 weeks and maintaining Step 12 for 16 weeks. Thus, the duration of Phase will vary from approximately 4 to 7 months, at which time the DBPCFC assessment will be completed and phase 2 intervention commenced.

The starting point in phase 1 (initial dose to be administered on the escalation day) will be individualised based on the outcome of the screening DBPCFC, as shown in Table 5. The NOAEL (No Observed Adverse Event Level or highest dose *not* triggering symptoms) will be used for this purpose, defined as the lowest dose tolerated at DBPCFC excluding transient Grade 1 symptoms (see Table 9).

Tolerated dose (NOAEL) at baseline DBPCFC	Initial dose for Phase 1		Max dose at Initial Escalation day		Max number of doses at initial escalation
	Step	CM Protein (mg)	Step	CM Protein (mg)	
<0.5mg (i.e. symptoms at first dose during DBPCFC)	1	0.01	7	1	7
0.5mg	5	0.2	8	2.5	4
3mg	6	0.4	9	6	4
10mg	8	2.5	10	15	3
30mg	9	6	11	30	3
100mg	10	15	12	60	3
300mg	11	30	12	60	2

Table 5. Starting dose for OIT in Phase 1.

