5.4 INTERIM POST-PHASE 1 ASSESSMENT (AROUND 6 MONTHS)

Subjects will be invited to undergo a DBPCFC to CM following completion of Phase 1 to again determine their threshold of reactivity to CM, according to Table 2 (Section 5.2.2). The pre-challenge assessment and challenge protocol are described in Section 5.2. Both challenge visits should take place with 28 days of each other. Subjects will also undergo repeat skin prick testing and HRQL assessments as described in section 5.8. Participants will continue their Phase 1 daily dosing until phase 2 is commenced.

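### The first challenge dose (0.5 mg) is watched for 60 minutes at baseline but for as little as 20-30 minutes at 6 months, so a few very sensitive children may be over-dosed and recorded a step too high

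*Combined protocol and SAP*

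**What the plan says.** Section 5.2 gives the purpose of repeating the challenge: "The DBPCFC will be repeated after each intervention phase to assess for any change in threshold". Section 5.4 has children challenged after Phase 1 "to again determine their threshold of reactivity to CM, according to Table 2", so both challenges use the same dose ladder.

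The ladder differs in one place. In Table 2 the minimum interval after dose 1 is "60 mins at baseline DBPCFC, 20-30 mins for 6m DBPCFC"; doses 2 to 7 carry the same 20-30 minutes at both challenges. The text of section 5.2.2 agrees with the table: "during the baseline DBPCFC, the dosing interval between the first (0.5mg) and second (3mg) doses will be extended to 60 minutes". It gives a safety reason: "The additional 30 minutes will allow for the detection of symptoms in the most sensitive participants", so that they are spared needless further milk. No reason is given for dropping the longer wait at 6 months.

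The same section allows discretion: "The time intervals following other doses may be extended up to one hour", where a reaction may be evolving.

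The 6-month result is used twice. Through Table 7 (section 5.5.1) it sets the Phase 2 starting dose. It also feeds a secondary efficacy outcome in section 3.1.2: "At least a 10-fold increase in eliciting dose (defined as the lowest dose which elicits objective symptoms or signs at challenge".

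**The concern.** A change score needs the same measurement at both ends. Here the only step that differs is the first one, which matters for the most sensitive children. Take a child who reacted to 0.5 mg at minute 45 at baseline, was allocated placebo, and is unchanged at 6 months. At baseline the reaction appears before any further milk is given. At 6 months the child may already have swallowed 3 mg, or 3 mg and 10 mg, when the symptoms start.

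Two things are at stake. The first is safety: the child receives milk that the baseline rule was written to withhold, although the protocol's reason for that rule still applies. The second is measurement: the reaction may be put down to a higher dose than the one that caused it, which would show a false rise in threshold and move the child up a row in Table 7.

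The children concerned are mainly in group C. Section 5.5 expects groups S and O to reach 60 mg daily by the end of Phase 1, far above 0.5 mg. Any misrecording would therefore tend to raise group C's apparent 6-month threshold and narrow its contrast with S and O.

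**Working it through.** **Inputs.** Table 2 doses: 0.5, 3, 10, 30, 100, 300, 1000 and 3000 mg. Interval after dose 1: 60 minutes at baseline, minimum 20-30 minutes at 6 months. Table 7 starting doses. Group size 22 (section 3). Planning expectation in section 5.5: 90% of children, even after placebo, tolerate 6 mg.

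**The plan's own figure.** 0.5 + 3 + 10 + 30 + 100 + 300 + 1000 + 3000 = 4443.5 mg, which matches the stated cumulative 4444 mg after rounding.

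**When the next doses fall at 6 months.** With spacing g, 3 mg is given at minute g and 10 mg at minute 2g. A reaction to 0.5 mg starting between g and 2g follows the 3 mg dose (one step up). One starting between 2g and minute 60 follows the 10 mg dose (two steps up).

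| Spacing | 3 mg at | 10 mg at | One-step window | Two-step window to minute 60 | Milk given before minute 60 |
|---|---|---|---|---|---|
| 20 min | 20 | 40 | 20-40 (20 min) | 40-60 (20 min) | 0.5 + 3 + 10 = 13.5 mg |
| 25 min | 25 | 50 | 25-50 (25 min) | 50-60 (10 min) | 13.5 mg |
| 30 min | 30 | 60 | 30-60 (30 min) | none | 0.5 + 3 = 3.5 mg |

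At baseline the amount given before minute 60 is 0.5 mg. Section 5.2.2 describes the baseline extension as an additional 30 minutes, which implies a usual interval of 60 - 30 = 30 minutes. The last row is therefore the expected case.

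**Effect on the 10-fold endpoint.** One step: 3/0.5 = 6-fold, which does not qualify. Two steps: 10/0.5 = 20-fold, which does. Each group C child with a two-step error would add 1/22 = 4.5 percentage points to that arm's 6-month rate. At 30-minute spacing the effect is 0.

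**Effect on the Phase 2 start (Table 7).**
- Correctly recorded (tolerated dose below 0.5 mg): start 0.04 mg, escalation-day maximum 2.5 mg.
- One step too high (tolerated dose 0.5 mg): start 0.2 mg, maximum still 2.5 mg.
- Two steps too high (tolerated dose 3 mg): start 0.4 mg, maximum 6 mg.

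**How many children.** The documents do not give the share reacting at 0.5 mg. The section 5.5 expectation leaves about 10% not tolerating 6 mg, or 0.10 x 22 = 2.2 per arm. That group also includes 3 mg reactors. If the share reacting at 0.5 mg is assumed to be 2%, 5% or 10%, the count in an arm of 22 is 0.4, 1.1 or 2.2. Only those still reactive at 6 months, with late onset and with the reaction put down to the later dose, would be misrecorded.

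**The case against.** The longer wait is a deliberate safety measure for the baseline challenge, when no child's threshold has yet been measured in the study; by 6 months every child has a result on file. That explains why the rule was written for baseline. It does not explain dropping it for a child whom the baseline result has identified as a first-dose reactor. The first row of Table 5 already marks these children: "<0.5mg (i.e. symptoms at first dose during DBPCFC".

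Existing wording might also cover the gap. Table 2 gives minimum intervals, so a cautious investigator can wait longer, and the discretionary extension can be read to include dose 1 at 6 months. Both are true, but neither obliges anyone to wait when the child has no symptoms at minute 20-30, and the discretion depends on a reaction that may be evolving.

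The objection that carries most weight is about recording. Section 5.2.4.1 has the apparent eliciting dose recorded, and section 3.1.2 defines it as the lowest dose that elicits objective signs. An investigator may therefore attribute a late reaction to 0.5 mg. A reader might infer that such children will certainly be recorded at the last dose given; the documents do not say so. They neither require nor forbid attribution to an earlier dose. This leaves misrecording possible rather than certain. It does not affect the extra milk, which has been swallowed either way.

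Any bias in group C's threshold would also work against showing a benefit of pretreatment, so it could not manufacture one in that comparison.

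**Conclusion.** The point holds as a small, cheap improvement. The intervals differ in both table and text, and nothing in the protocol requires a longer wait at 6 months for a symptom-free child known to react at 0.5 mg. Such a child can receive 3.5 mg, or 13.5 mg at 20- or 25-minute spacing, in the hour during which baseline allowed only 0.5 mg. The recorded threshold may then be 6-fold too high, or rarely 20-fold.

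A reader might infer that the 6-month efficacy results are unreliable or that Phase 2 starts become unsafe. The documents support neither reading. The usual one-step error misses the 10-fold endpoint, and the two-step error cannot occur at 30-minute spacing. Recorded doses of 3 or 10 mg are far below the 1.4 g and 8 g criteria. Both shifted Phase 2 starts stay below 0.5 mg, and escalation-day doses are supervised and stopped for significant symptoms. The primary outcome and the sample size are essentially unaffected.

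The size, probably 0-2 children per arm or fewer, rests on a planning expectation about 6 mg rather than on a count of 0.5 mg reactors, and the documents give no onset times. The gain is mainly safety and like-for-like measurement in the most sensitive children.

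**What to change.** In Table 2, keep the 60-minute interval after dose 1 at the 6-month challenge for every child whose baseline eliciting dose was 0.5 mg, regardless of arm. Apply it on both the milk and the placebo day, so that the wait does not reveal which day is which. The rule uses baseline data only, so Phase 1 allocation also stays concealed. For consistency the same rule may be applied at the exit challenge (Table 3), though little effect is expected there after 6 months of OIT.

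The cost is a one-line edit. Each visit lasts 60 - 30 = 30 to 60 - 20 = 40 minutes longer, so the two 6-month visits add 60-80 minutes per affected child. If as many as 10% of the 66 children (6.6) were affected, the total would be 6.6 x 60 minutes = 6.6 hours to 6.6 x 80 minutes = 8.8 hours, or about 7-9 visit-hours across the trial. No extra procedure is needed.

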5.2.3 EXIT DBPCFC AT 12 MONTHS

The challenge will consist of up to nine consecutive, increasing doses of CM (or placebo) at 20-30 minute intervals, up to a cumulative dose of 8 gram CM protein, as shown in table 3.

Exit DBPCFC to Cow's Milk		
Dose	CM protein (mg)	Approx. volume of CM (ml)
1	0.5	0.015
2	3	0.09
3	10	0.3
4	30	0.9
5	100	3
6	300	9
7	1000	30
8	3000	90
9	3600	105
Cumulative dose	8044	250
2 hours observation period following last dose to monitor for signs of reaction		

Table 3. Dosing protocol for exit DBPCFC to CM.

5.2.4 ASSESSMENTS DURING FOOD CHALLENGES

The baseline food challenges are categorised as 'high-risk' on the basis that we expect the challenges to be positive. To minimize risk to the patient, all challenges will take place in a clinical environment where food challenges are performed on a regular basis, and staff are familiar with the management of allergic reactions including anaphylaxis through clinical experience and regular training.

The clinical team may elect to secure intravenous access by cannulation as an additional safety precaution at challenge. This will allow treatment to be easily and rapidly administered in the event of a significant allergic reaction, and also allows blood to be collected without further venepuncture. In order to minimize discomfort to the child, we will offer local anaesthetic cream to be applied at least 30 minutes prior.

At both sites, blood (up to 30ml, equivalent to 1.5ml/kg) will be collected at baseline, 6 and 12 months for laboratory assessments relating to CM allergy and assessment of tolerance (see section 5.7.2). The baseline blood sample may be collected at the screening visit, or deferred to the initial DBPCFC where it can be taken from the intravenous cannula, thus reducing the number of blood tests / needle-sticks required. The blood sample will be used to provide baseline haematology (blood count) and for mechanistic investigations (as outlined in section 5.8.3).

In the London centre, additional blood samples will be collected at the initial baseline DBPCFC visits, prior to the start and during the challenge via the cannula, in order to confirm a clinical reaction using objective laboratory assessments. Since the cannula will already be sited, this will not cause discomfort to the child; where the cannula does not bleed back, no further venepuncture will be attempted. A maximum total volume of 2.5ml/kg (max 100ml) blood will be collected per visit. The blood volume is consistent with national and international guidelines on the volume of blood which can safely be taken from a child.¹²

During DBPCFC, participants will be monitored including heart rate, blood pressure and oxygen saturations. PEFR will be assessed prior to challenge, and should be repeated in the event of any respiratory symptoms or at the study team's discretion. Clinical manifestations will be assessed throughout the challenge.

Skin prick testing to fresh CM and commercial CM extract (together with positive and negative control) will be performed prior to each baseline DBPCFC. The wheal response will then be measured at approximately 30 minute intervals thereafter, until the wheal has reduced to 3mm or less, or the patient is discharged (see section 5.8.1).

